## IX. Description of statistical analysis

The higher doses we propose, with 4,000 or 10,000 IU/d are expected to maximize the vitamin D treatment effect if one exists compared to a lower high dose as in a Harvard study currently underway which explores 2,000IU/day vitamin D. While the Harvard study gives vitamin D in the context of acute infection or household exposure so vitamin D levels may not respond quickly enough to affect outcomes (perhaps both for treatment and prevention), our proposed design seeks to raise vitamin D levels in advance of sustained risk in a set of HCWs and other community members at increased risk of COVID-19, increasing both the likelihood of having therapeutic dosing and the underlying risk of COVID-19 that increase the expected treatment effect, and therefore increases overall statistical power.

For our primary outcome of COVID-19 infection as measured by patient report of clinically confirmed COVID-19 (or viral PCR when available) and secondary outcomes of COVID-19 antibody seroconversion and disease severity (hospitalization, ICU stay, ventilator use, death), hazard models will be employed to assess the effect of each vitamin D dosing strategy on the outcome. We will first develop hazard ratios for between-group analyses on the primary outcome using log-rank tests, and then develop Cox proportional hazard models to model the hazard function on a set of covariates including but not limited to, moderate or high vitamin D dose, baseline vitamin D levels, age, gender, race, ethnicity, sun exposure, sleep habits, exposure of cohabitants, job type, and study site. We will also control for randomization date to adjust the underlying hazard function for COVID-19 prevalence over time. While our primary analysis will pool subjects randomized to either the moderate or high dose and compare them to low dose subjects, we will also perform secondary analyses comparing low to moderate and low to high and additional analyses that use post randomization vitamin D levels as time varying covariates. The design thus seeks to maximize potential to find statistically significant results between different dosages given uncertainty in subject willingness to be randomized to different doses. As noted above, the sample size was chosen to have at least 80% power to detect a 25% or larger decrease in the hazard of developing COVID-19 between study arms at  $p<0.05$  assuming a 30% baseline 10-month COVID incidence over the study period, in line with the 3% monthly incidence cited above. As finding that a higher dose has no effect or a paradoxical adverse effect on COVID incidence would both lead to use of a lower dose given even the small risks of higher dose vitamin D, Ruxson and Neuhauser would argue for use of a 1-sided test, resulting in 80% power to detect a 20% or larger decrease.

The proportional hazards assumption will be assessed using the *estat phtest* command in Stata with rejection of proportion hazards defined by  $p<0.05$  for any variable or the global test, or by visual assessment of Schoenfeld residuals. Continuous variables which fail proportional hazards will be categorized. For any categorical variable or categorized continuous variable which fail proportional hazards, we will perform Cox regression which stratifies based on that variable. If moderate or high dose vitamin D variables fail the proportional hazards assumption, we will estimate non-proportional hazards models. Assuming missingness at random, we will impute missing values of covariates with multiple imputation by chained equations with 20 imputations. Covariates in the imputation will include the covariates in the primary analysis excluding moderate or high dose vitamin D variables. Data analysis will be executed in Stata 18.0.

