## II. Purpose

We propose to seek to recruit participants to be randomized to low versus high (10,000 IU/day) or low versus moderate (4,000 IU/day) dose vitamin D and pool these populations for our primary analyses. The study will focus on health care workers and other individuals from Chicagoland communities with elevated risk of exposure to COVID-19. In addition to their high exposure rates to COVID-19, focusing on health care workers is also useful because they have high rates of vitamin D deficiency due to indoor work and long hours, are likely to tolerate high doses of vitamin D given their generally good health, and have ready access to monitoring for dose toxicity. In addition to HCWs, we have decided to expand our focus to include other adults in Chicagoland communities. Due to vaccine distribution in the coming months prioritizing HCWs, we want to offer the potential benefits of vitamin D in COVID-19 prevention to those who will not have prioritized access to vaccines, or choose to be vaccinated at present. **Thus, our overall aim is to compare the risks of COVID-19 in health care workers and other Chicagoland adults at increased risk of COVID-19 randomized to low (400 IU/day) vs. moderate (4,000 IU/day) or high (10,000 IU/day) dose vitamin D. Our specific aims are:**

**Aim 1:** To compare the risk of developing COVID-19 in health care workers and other Chicagoland community members at increased risk of COVID-19 randomized to low vs. moderate or high dose vitamin D. We hypothesize that moderate and high dose therapy will reduce rates of COVID-19 compared to low dose therapy because vitamin D will reduce symptomatic infection that prompts testing for COVID-19. Our primary analysis will pool subjects randomized to the moderate or high dose and compare them to low dose subjects, with secondary analyses comparing low to moderate and low to high. The design thus seeks to maximize potential to find statistically significant results between different dosages given uncertainty in subject willingness to be randomized to different doses.

**Aim 2:** To compare COVID-19 seroconversion in health care workers and other Chicagoland community members at increased risk of COVID-19 randomized to low vs. moderate or high dose vitamin D. As we suspect the main effect of vitamin D may be to decrease symptomatic disease we hypothesize that there may be little or no difference in seroconversion.

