The intake survey will collect baseline data on subjects' current medications and supplements with doses (e.g., multivitamin, zinc, calcium, vitamin D), average time outside per day (specifying direct vs. indirect sun exposure), Fitzpatrick skin type, exercise habits, diet, sleep habits, possible COVID-19 symptoms such as fever, cough, GI problems, and other influenza-like symptoms. Subjects will also be asked to report suspected exposure to the virus (e.g. if a family member falls ill), specific occupation, and demographic information. Subjects will also be asked to evaluate risks of exposure. Participants will also be asked in the intake surveys for the name and contact of information of 1-2 people who could reach them and answer follow-up questions if they cannot be reached or answer questions themselves. Follow-up surveys at months 3, 6, and 9 will ask the participant (or proxy if needed) whether the participant has had a clinically confirmed diagnosis of COVID-19, and the date if so, ask about rates of study medication adherence, and assess for changes in the intake questions about use of other supplements, sun exposure, diet, exercise, and COVID-19 exposures. If the patient is reported to have had COVID-19, we ask about severity, including hospitalization and duration, ICU-use and duration, and need for mechanical ventilation and duration, death and COVID-19 symptom severity using the BEAT-19 adapted to reflect the worst symptomology during their period of active COVID-19. In addition to these questions, we have added some questions on the baseline and follow-up surveys that evaluate additional possible risk factors for COVID-19 outcomes. These risk factors—hypertension, diabetes, and mood—are shown to have possible linkages to vitamin D levels. These factors are receiving increased attention in the context of COVID-19 risk and its relationship to low vitamin D levels. While available evidence suggests there is a link between hypertension/cardiovascular disease, diabetes and metabolism, depression/anxiety, and vitamin D levels, to-date no causal relationship has been established. This is supported by both evidence as recently as this year, as well as earlier studies. Questions about hypertension and diabetes are of our own construction, and questions about depression and anxiety come from validated instruments, the GAD-2 and the PHQ-2. We hope to shed light on the relationship between our outcomes of interest, vitamin D, and these risk factors by asking subjects, both already enrolled and new, about these factors.

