**Table 1: Subject timeline in study: For subjects recruited before January 1, 2022**

Date	Activity	Description
Baseline (Month 0)	Recruitment and enrollment	
 
Subjects will be screened for eligibility, undergo initial blood draws, and undergo randomization.
 
Subjects will be given 9-month supply of vitamin D with instructions for daily intake. Subjects will complete the intake survey via telephone or web.
 

Month 3	Wave 1	
 
Subjects will visit the lab for their follow-up Wave 1 blood draws. CRCs will call or email subjects to remind them of the lab visit as needed until the lab visit is confirmed completed.
 
Subjects will also be sent the first follow-up web-based survey via email or text message. CRCs will call and email subjects as needed to remind them to complete the survey.
 

Month 6	Wave 2	
 
Subjects will visit the lab for their follow-up Wave 2 blood draws. CRCs will call or email subjects to remind them of the lab visit as needed until the lab visit is confirmed completed.
 
Subjects will be sent the second follow-up web-based survey. CRCs will call and email subjects as needed to remind them to complete the survey. For the 6-month subject cohort, this set of labs will be their final set of labs and surveys.
 

Month 9	Wave 3	
 
Subjects in the 9-month cohort will visit the lab for their final blood draws in this wave. CRCs will call or email subjects to remind them of the lab visit as needed until the lab visit is confirmed completed.
 
Subjects will also be sent the final follow-up web-based survey. CRCs will call or text subjects to remind them to complete the survey.
 

Months 10-23	Final analysis & chart review	
 
Final analyses and reporting of the intervention effects on outcome measures will take place during this period to prepare for dissemination.
 
Chart review evaluating outcomes (e.g., hospitalization, positive COVID test)
 

		
 
For both the 6-month and 9-month cohorts, chart review will occur for 12 months after their participation
 

--	--	---

**Table 2: Subject Timeline in Study: For subjects recruited in the study on or after January 1, 2022 but before March 31, 2022**

Date	Activity	Description

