## VII. Description of experimental controls and use of placebos

In this 2,000-person two-arm, double-blinded randomized controlled trial, we will randomize half the subjects to low dose vitamin D therapy (400 IU/day), which will serve as the control group, and half to moderate (4,000 IU/day) or high (10,000 IU/day). Participants will have the option of being randomized to the high versus low strategy or the moderate versus low strategy. The low dose was selected to ensure that all subjects had a high likelihood of a total vitamin D intake that met the recommended daily allowance (RDA).

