## VIII. Type and number of experimental subjects

We plan to recruit 2,000 health care workers and other Chicagoland community members. HCWs will be primarily employed at the University of Chicago Medicine (UCM)- Hyde Park, River East, or Ingalls, and Rush University (RU) at the Rush University Medical Center, Rush Oak Park Hospital, and Rush South Loop clinics. At UCM, ~250 HCWs have been diagnosed with COVID-19 as of late June, out of a reduced pool working non-remotely of about 3,000 persons over 4 months, for a monthly incidence of about 2% of working HCWs per month. During the summer months, as COVID-19 rates declined and stabilized in Chicago, the monthly incidence at UCM has fallen to about 1% per working HCW per month, but this reflects continued closure of most ambulatory services, which are now among the highest risk services given COVID-19 testing of all inpatients but not outpatients. Indeed, our inpatient COVID-19 unit has reported zero HCW infections. Thus the relative odds of infection appear to be several times higher in high risk HCWs than low risk HCWs. In the presence of appropriate personal protective equipment, high risk HCW groups based on the UCM experience and the literature are persons working in high volume ambulatory settings (e.g., primary care, ophthalmology), the emergency department, radiology, respiratory services, nursing, patient transport, custodial and food services. We will prioritize recruitment of these groups, and since ambulatory care is rapidly reopening now, we think that 3% is a reasonable estimate for the baseline monthly incidence in our study subjects. We think this is a conservative estimate as it is similar to the rate in the general local population. As COVID-19 infection rates have spiked in Chicago and neighboring communities over the past few months, the vast majority HCWs who test positive report community exposure, predominantly from transmission in their household or from those in their close

social network. Further, since two COVID-19 vaccines are now available we will expand our population to also include Chicagoland community members, who continue to be at increased risk for COVID-19 infection, with increased rates from 15 to 70 per 100,000 in recent months, trust gaps in vaccines, and lower priority access to vaccines for many outside the health care/front line professions—all resulting in potential lower rates of vaccination among the general population and a continued risk of infection.

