The sample size was chosen to have at least 80% power to detect a 25% or larger decrease in the hazard of developing COVID-19 between study arms at  $p<0.05$  assuming a 30% baseline COVID-19 incidence rate over the study period, in line with the 3% per month incidence cited above.

*Individuals are eligible to enroll in the study if they:*

1. Are 18 years or older.
2. Live or work in the Chicagoland area (Illinois counties: Cook, Lake, McHenry, DuPage, Kane, Kendall, Grundy, Will, and Kankakee; Indiana counties: Lake and Porter).
3. Are interested in vitamin D as a potential preventive measure against COVID-19 in which they self-administer a daily dose of vitamin D during the 9-month study period.
4. Are willing to attend the laboratory for drop-in appointments at UChicago Medicine, Ingalls Hospital, or Rush University Medical Center every 3 months at up to 4 time points over up to a 9-month period for blood draws measuring COVID-19 antibodies, calcium, vitamin D and PTH levels.
5. Are willing to complete self-report measures at up to 4 time points over the course of up to 9 months by completing a 15-minute survey at intake by telephone or via web and 10-minute web-based follow-up surveys.

*Individuals are excluded from the study if they:*

1. Report being pregnant, planning to become pregnant, and/or report breastfeeding during the study period.
2. Report a history of chronic kidney disease, including a history of abnormal GFR and/or creatinine.
3. Report a history of hyperparathyroidism.
4. Report a history of increased falls.
5. Report a history of hypercalcemia.
6. Report a history of gastrointestinal absorptive disorders, including having undergone bariatric surgery.
7. Report a history of kidney stones (1 in past year or 2 in lifetime).

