At the beginning of the consent process, subjects will be asked to verify their identity by emailing or texting the study email or study cell phone a photo of their diver's license, state ID, passport or employee ID. They will be asked for their email address where a signed copy of the consent form will be sent for their records. In the consent form, subjects will be informed about the nature of the intervention, that they will be receiving a daily dose of vitamin D, either low or moderate/high, and must self-administer this dose each day. They will be informed about the nature of the intervention, that they are blinded to the dose they receive. Subjects will be reminded that participation is entirely voluntary, and they may withdraw at any time without consequence. Subjects will also be informed about the data collection methods, including the survey and testing they will undergo at each stage, and that they will be informed about test results for COVID-19 antibodies only during the study period. They will be informed that their PTH, calcium and vitamin D results will be withheld until completion of study participation unless they suggest a safety concern. They will be educated about the risks of the study as described above in "Potential Risks". Subjects will be informed about what will be done if they are found to be hypercalcemic: First, they will be told to cease vitamin D supplementation. Subjects at UCM with a calcium level 10.5-12 mg/dL and at Rush with a calcium level 11.3-12mg/dL will be instructed to consult with their primary care physician. All subjects with a calcium level of 12.1-14 mg/dL will be referred to urgent care. All subjects with a calcium level greater than 14 mg/dL will be referred to the emergency room. These participants will continue to undergo monitoring blood draws and surveys and may resume vitamin D supplementation per study protocol with a physician note.

Subjects will then be instructed to select their randomization preference on the consent form. If a potential subject says they are already taking a supplement or supplements that contains 2,000IU or less of vitamin D in total, they may continue to take those supplements while part of the study, however, they will only be allowed to enroll in the arm that randomized them between 400 and 4,000IU.

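### The primary event definition does not keep out infections that a participant knows of only from the study's own disclosed antibody result, which belong to Aim 2

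*Combined protocol and SAP*

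**What the plan says.** **Primary event.** Section IX (statistical analysis) counts "patient report of clinically confirmed COVID-19 (or viral PCR when available". It lists antibody seroconversion separately, as a secondary outcome. No section defines *clinically confirmed*.

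**How it is captured.** Section III, Procedures and Materials, says the follow-up surveys ask "whether the participant has had a clinically confirmed diagnosis of COVID-19, and the date if so". Severity and symptoms are asked about when COVID-19 is reported. The type of test or other basis of the diagnosis is not among the listed items. The same section says that participants self-report positive PCR results each quarter.

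**What participants learn.** Section XIV (consent) says "they will be informed about test results for COVID-19 antibodies only during the study period", while PTH, calcium and vitamin D are withheld unless there is a safety concern. Procedures and Materials agrees: its list of blinded results covers vitamins A and D, calcium and PTH, but not antibodies. Antibodies are measured at each scheduled draw, whether or not there are symptoms.

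**Expected effects.** For Aim 1, Section II expects that "vitamin D will reduce symptomatic infection that prompts testing for COVID-19". For Aim 2 it says, in hedged terms, that seroconversion may hardly differ between arms.

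**The concern.** Take a participant who has no symptoms, is antibody-positive at the month 3 draw, is told so, and answers yes to the diagnosis question at month 6. By the aims, this is a seroconversion. By the wording of Section IX it can be counted as a primary event, because a patient report suffices and nothing excludes one that rests on the study's own test. Its date would be tied to the quarterly draw rather than to the infection, and that date enters the Cox model.

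What matters is the contrast between arms. If the higher doses prevent symptoms more than infection, silent infections show a weaker effect than symptomatic ones, and mixing them in moves the Aim 1 hazard ratio up, toward 1. If some symptomatic infections become silent ones while total infections stay equal, silent infections are more frequent in the higher-dose arm, and the shift is larger than simple dilution. A null Aim 1 result would then be harder to interpret.

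**Working it through.** **Inputs from the documents.** Section VIII: "We plan to recruit 2,000 health care workers and other Chicagoland community members". Section VII: "we will randomize half the subjects to low dose vitamin D therapy (400 IU/day), which will serve as the control group". This gives 1,000 per arm. Section VIII claims "at least 80% power to detect a 25% or larger decrease in the hazard of developing COVID-19 between study arms at" the 0.05 level with 30% control incidence. I take the test as two-sided.

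**Inputs not in the documents (assumed).** The share *f* of silent infections reported as a diagnosis; the total infection risk *q*, or the silent infection risk *s*.

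**Formulas.** Hazard ratio = ln(1 - p_high) / ln(1 - p_low). Events D = 1000 × (p_low + p_high). Power = Φ(√(D/4) × |ln HR| - 1.96).

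**Step 1: the plan's own case.** p_low = 0.30; p_high = 1 - 0.70^0.75 = 0.2347; D = 534.7. Power = Φ(11.56 × 0.2877 - 1.96) = Φ(1.37) = 91.4%. The stated floor of 80% is met, with no allowance for dropout.

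**Step 2: silent infections equal in both arms.** Observed risk = p + f × s. With s = 0.10 and f = 0.25: 0.325 against 0.2597, HR 0.765, D = 584.7, power 89.9%.

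**Step 3: total infections equal in both arms.** Observed risk = p + f × (q - p). With q = 0.40 and f = 0.25: 0.325 against 0.2347 + 0.25 × 0.1653 = 0.276; HR = ln(0.724)/ln(0.675) = 0.822; D = 601; power 67.2%.

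| Assumption | f | HR | Power |
|---|---|---|---|
| None reported | 0 | 0.75 | 91% |
| Equal silent infections, s = 5-20% | 25% | 0.76-0.78 | 89-91% |
| Equal total infections, q = 35-50% | 10% | 0.78-0.79 | 83-84% |
| Equal total infections, q = 35-50% | 25% | 0.82-0.83 | 65-68% |

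Under equal total infections, power reaches 80% when *f* is about 13-15%. If vitamin D lowered the hazards of silent and symptomatic infection equally, the hazard ratio would stay at 0.75.

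**Step 4: how large *f* can be.** Draws and surveys fall in the same wave (Section IV, Tables 1 to 4). Assume that results come back after that wave's survey and that infections are spread evenly over follow-up. Then seroconversions first seen at the last draw cannot be reported. About 2/3 of silent infections are reachable in the 9-month cohort, 1/2 in the 6-month cohort, and none in participants with a single follow-up wave. An overall *f* of 25% then needs 0.25/(2/3) = 37.5% of reachable cases reported in the 9-month cohort and 0.25/(1/2) = 50% in the 6-month cohort. The note after Table 4 says overdue final surveys are still pursued, which loosens this limit somewhat.

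**The case against.** The strongest reply is that the text already points away from antibody-only reports. Procedures and Materials speaks of self-reported PCR positives, and in ordinary usage a research antibody result is not a clinically confirmed diagnosis. Many participants would read the question that way. This stands as a reason to expect a modest *f*. It does not close the route: the PCR sentence describes what is reported, while the survey question and Section IX use the broader term and Section IX makes PCR optional.

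A second reply is that Aim 1 concerns the risk of COVID-19, and that Section IX calls the outcome infection. This also stands. A reader might infer that any silent infection is a false Aim 1 event. The documents do not support that: participants are told to seek PCR after exposure as well as for symptoms, so silent infections found by PCR count by design. The narrower point is that the study's own scheduled antibody test, whose result the plan assigns to Aim 2, can feed the self-reported Aim 1 event.

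A reader might also infer that chart review opens the same route just as widely, because Tables 1 to 4 mention "Chart review evaluating outcomes (e.g., hospitalization, positive COVID test" without specifying a viral test. The documents do not show this. The phrase is an example in a timeline, Section IX does not name chart review as a source of primary events, and no section says that study antibody results enter the medical record.

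**Conclusion.** The gap is real, and closing it is a worthwhile, cheap improvement. Results are disclosed, the event is self-reported, its basis is not recorded, and no rule keeps antibody-only reports out of Aim 1. The direction, toward 1, holds if the effect on silent infection is weaker than on symptomatic infection. Section II suggests this but does not assert it.

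The size cannot be derived from the documents. A reader might infer from the 65-68% row that Aim 1 is underpowered. That does not follow: the row needs exactly equal total infections and a quarter of all silent infections reported, despite the timing limit. At 10% reported under the same assumption, or at 25% with equal silent infections, power stays above the stated 80%.

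**What to change.** **Definition.** Reconcile Procedures and Materials with Section IX. A primary event should rest on a positive viral test or on a clinician's diagnosis made independently of the study's antibody test. Antibody-only reports count for Aim 2 only. If chart review contributes primary events, say that the test must be viral.

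**Survey.** Add one follow-up item on the basis of the diagnosis (viral test, clinician, study antibody result), with an instruction not to count the study antibody result.

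**Surveys already collected.** Keep the original count. Add a sensitivity analysis, with review blinded to arm, that sets aside reports meeting both conditions: the diagnosis date (not the survey date) falls on or after a disclosed positive study antibody result, and there are no reported symptoms, viral test or clinician record. This should not replace the original count, because true cases also seroconvert and outside PCR records may be missing.

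**Cost.** Wording, one survey item and one analysis rule; no new visit, sample or participant. The small downside is that a few true cases without such records may be set aside in the sensitivity analysis.
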